2.1 Primary Efficacy Endpoint

The Unified Parkinson’s Disease Rating Scale (UPDRS) is a comprehensive assessment of the burden and severity of signs and symptoms of parkinsonism captured via systematic interview and neurological examination. It consists of 4 parts that can be used as individual scales or summed for a total score.

Part II of the UPDRS is an in-depth health outcome assessment of motor activities of daily living that are impaired by a wide range of neurological diseases, including PKAN. For this study, Part II of the UPDRS has been adapted and validated for use in PKAN

patients through a systematic, iterative process involving experts and patient advocacy leaders; it is the basis of the primary efficacy endpoint and will be referred to in this SAP as the “PKAN Activities of Daily Living” scale, abbreviated as “PKAN-ADL”.

The primary efficacy endpoint is the change in PKAN-ADL total score, from baseline to the end of the 24-week double-blind period.

2.2 Secondary Efficacy Endpoint

The secondary efficacy endpoint is the change in the total score for Part III (motor examination) of the UPDRS from baseline to the end of the 24-week double-blind period.

2.3 Exploratory Efficacy Endpoints

Exploratory efficacy endpoints will include change from baseline to the end of the 24-week double-blind period in the following:

- Clinician Global Impression of Improvement (CGI-I)
- Barry Albright Dystonia (BAD) scale
- Quality of life (QoL):
 - NeuroQoL, upper and lower extremity modules (adult and pediatric versions)
 - EuroQol 5-dimension, 3 level QoL instrument (EQ-5D-3L)/EuroQol-5D Youth Version (EQ-5D-Y)
- Functional independence: Functional Independence Measure (FIM)/Functional Independence Measure for Children (WeeFIM)
- Function measures:
 - Ambulation: 25-foot walk test (in appropriate patients)
 - Speech: Diadochokinetic (DDK) assessments (i.e., alternating motion rate [AMR] and sequential motion rate [SMR])

2.4 Safety Endpoints

The safety and tolerability of fosmetpantotenate will be assessed based on the occurrence of adverse events (AEs) and by serial vital signs including weight, physical examinations, clinical laboratory parameters (chemistry, hematology, coagulation, and urinalysis), the Columbia Suicide Severity Rating Scale (C-SSRS) (in assessable patients), and 12-lead electrocardiograms (ECG).

2.5 Pharmacokinetic Endpoints

Multiple dose PK of fosmetpantotenate in whole blood will be evaluated using a sparse sampling design. Blood samples may also be used for metabolite quantification and/or identification.

2.6 Biomarkers

Exploratory biomarkers will be assessed in plasma. Potential biomarkers assessed may include succinate, lactate, maleate, pyruvate, alanine, acetone, acetoacetic acid, 3-hydroxybutyric acid, 2-hydroxybutyric acid, and acetylCoA. Although other biomarkers may be assessed, the samples will not be used for genetic testing.

2.7 Pharmacogenomics

Pharmacogenomic assessment may be performed on blood samples drawn at screening for drug metabolizing enzymes, transporters, or indicators of therapeutic response or safety. These assessments will only be performed where local regulations permit and where approved by the site's Institutional Review Board/Independent Ethics Committee (IRB/IEC), and will be subject to separate consent/assent by the patient/parent/legal guardian as appropriate.

3 Overall Study Design

This is a pivotal, randomized, double-blind, placebo-controlled, multi-center, 2-arm study evaluating 24 weeks of treatment with fosmetpantotenate or placebo in patients with PKAN aged 6 to 65 years, with a 278 week open-label extension.

Eligible patients will be randomized in a 1:1 ratio to receive either fosmetpantotenate or placebo for a 24-week double-blind period; randomization will be stratified by screening weight and age group (pediatric, adult), as reported by Interactive Web Response System (IWRS). In Protocol Version 1, Pediatric is defined as ' <19 ' and Adult is defined as ' ≥ 19 .' In subsequent versions of the Protocol, Pediatric is defined as ' <18 ' and Adult is defined as ' ≥ 18 '.

Treatment in the double-blind period will begin with dose escalation for Days 1-3, followed by the full dose 3 times daily (TID) starting on Day 4. Matching placebo will be given according to the same dose escalation sequence as active investigational product. Study visits during the double-blind period are scheduled at baseline (within 1 to 2 days prior to the start of the double-blind treatment), Days 1 through 4, and Weeks 3, 6, 12, 18, and 24. See Protocol Appendix A ([Table 15.1-1](#)) for the schedule of assessments performed during the double-blind period.

After completing the double-blind period, patients will be eligible to receive open-label fosmetpantotenate for up to 278 weeks. During the open-label period, study visits are scheduled at Weeks 27, 30, 36, 48, 60, 72, 84, 96, 108, 120, 146, 172, 198, 224, 250, 276, and 302. See Protocol Appendix A ([Table 15.1-2](#)) for the schedule of assessments performed during the open-label period.

In total, patients will be in the study for approximately 302 weeks, with 24 weeks in the randomized, double-blind treatment period and 278 weeks in the open-label period.

4 Statistical Methodology

This section describes the planned methods of analysis for all efficacy and safety endpoints collected during the double-blind and open-label extension periods.

4.1 General Statistical Considerations

Tabulations of summary statistics, graphical presentations, and statistical analyses will be performed using SAS® Version 9.3 or higher. All data collected will be summarized using descriptive statistics, including mean, standard deviation (SD), median, minimum, and maximum for continuous variables, and frequency tables with counts and percentages for categorical variables. Age group categorization will be consistent with the Protocol Version that was applicable at time of patient randomization.

Unless otherwise stated, the “baseline” assessment for the double-blind period will be defined as the last measurement obtained prior to the first dose of blinded investigational product (pre-dose on Day 1). For patients who enter the open-label extension period, the baseline value will be re-defined for the open-label period as the last observation prior to start of open-label fosmetpantotenate, unless otherwise specified.

As appropriate, the scales used as efficacy endpoints to measure neurological impairment, dystonia, motor function, and quality of life will be scored and/or normalized in accordance with user manuals and published scoring procedures for each instrument. For each scale, the prescribed rules for deriving the total score in the presence of 1 or more missing items will be followed.

Unless otherwise noted, if at least 80% of the items for a scale (i.e., PKAN-ADL, UPDRS Part III, BAD, Neuro-QOL) are non-missing, then the prorated total score for the scale is obtained by summing the non-missing item responses, multiplying by the total number of items in the scale, and then dividing by the number of non-missing items.

There are two patients who had a question (item) on the PKAN-ADL mistranslated for screening and baseline visits. In analyses using the Double-Blind Full Analysis Set, the values for this item will be rendered invalid, set to missing, and the PKAN-ADL total score will be prorated as described above. The invalid values will be presented and flagged in the data listing, as originally recorded.

For by-visit summaries, the last non-missing assessment (including repeat assessments, if any) recorded at each visit will be used for summarization. For across visit summaries (e.g. maximum post-baseline value), scheduled, unscheduled (if any) and repeat assessments will all be considered for the value to be analyzed; all observations will be presented in data listings.

Hypothesis-testing will be performed at the two-sided 5% significance level, unless otherwise stated.

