4.4 Data Sets Analyzed

The following analysis sets will be defined for this study:

Double-Blind Period

Double-Blind Safety Population: The Double-Blind Safety Population will consist of all patients who receive at least 1 dose of blinded investigational product. Patients will be analyzed according to the treatment received. This population will be used for all summaries of patient accountability, demographic and baseline data, and safety information, including AE incidence, for the double-blind period of the study.

Double-Blind Full Analysis Set (FAS): The Double-Blind FAS will consist of all randomized patients with a baseline assessment and at least 1 post-baseline assessment of the primary efficacy endpoint. Patients will be analyzed in the treatment group to which

they were randomized, regardless of treatment actually received. This population will serve as the basis for all efficacy analyses for the double-blind period of the study.

Double-Blind Per-Protocol Set (PPS): The PPS will consist of all FAS patients who complete the double-blind study without any major protocol violations that could impact the interpretation of efficacy. Patients will be analyzed as randomized. This population will be used for sensitivity analyses of the primary and secondary efficacy endpoints (based on PKAN-ADL and UPDRS Part III scores). Specific protocol deviations used to define this analysis set will be finalized prior to database lock.

Open-Label Period

Open-Label Safety Population: The Open-Label Safety Population will consist of all patients who receive at least 1 dose of investigational product after entering the open-label period of the study. This population will be used for all summaries of patient accountability, demographic and Baseline data, and safety information, including AE incidence, for the open-label period of the study.

Open-Label Full Analysis Set (OL-FAS): The OL-FAS will consist of all patients with a baseline assessment and at least 1 post-baseline assessment of the PKAN-ADL in the open-label period of the study. This population will serve as the basis for efficacy analyses from the open-label period of the study.

Fosmetpantotenate Safety Population: The Fosmetpantotenate Safety population will consist of patients who received at least 1 dose of fosmetpantotenate product at any period of the study (double-blind or open-label).

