4.10.1 Primary Efficacy Endpoint

The PKAN-ADL consists of 12 items related to activities of daily living, including eating, dressing, and walking. Each item has responses ranging from 0-4, with a higher value indicating greater disability in the given activity. To compute the total score, responses are summed across the 12 items.

For analysis purposes, data from the pediatric and adult age groups will be pooled. All descriptive summary tables will be repeated using age group as a subgroup.

Descriptive statistics will be presented for the PKAN-ADL total score, with absolute and percent change from baseline, by treatment group for each visit of the double-blind

period. For post-baseline assessments, categories for change from baseline total score (e.g., >0 , $=0$, <0 , ≤ -1 , ≤ -2 , ≤ -3 , ≤ -4), categories for percent improvement (i.e., decrease) in total score from baseline (i.e., $<0\%$, $=0\%$, $>0\%$, $\geq 10\%$, $\geq 20\%$, $\geq 30\%$, $\geq 40\%$, $\geq 50\%$), and categories for total score status (improvement, no change, or worsening) will be presented. These categories may be adjusted in a way that ensures that the categories contain at least 10% of patients. This will be run using the Double-Blind FAS, and repeated using the PPS, as a sensitivity analysis.

Change from baseline will be calculated by subtracting the baseline total score from the post baseline total score. Percent change from baseline will be calculated as:

$$100 * (\text{Observed Score at Post-Baseline Visit} - \text{Observed Score at Baseline}) / \text{Observed Score at Baseline}$$

Furthermore, a chi-squared test will be performed at each post-baseline visit to determine treatment differences between the percentages of patients who had a total score indicating improvement, no change, or worsening. Proportions, with estimated 95% CI, will be reported for each treatment group, along with a p-value corresponding to the treatment comparison.

Frequency tables will display change from baseline for each of the 12 items, as well as shift from baseline, by treatment group for each post-baseline assessment of the double-blind period. In addition, categories for change from baseline item score (i.e., >0 , $=0$, <0 , ≤ -1 , ≤ -2 , ≤ -3), and categories for item score status (improvement, no change, or worsening) will be presented. These summaries will be run using the Double-Blind FAS and repeated using the PPS, as a sensitivity analysis.

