Figures will be presented which show the PKAN-ADL total score for each visit during the double-blind period, as well as change from baseline score, by treatment group. This will be run using the Double-Blind FAS and repeated using the PPS.

In addition, a by-patient listing will be provided, which presents PKAN-ADL scores (total and for each item) across all assessments in the double-blind and open-label periods for patients in the Double-Blind FAS.

The change from baseline in PKAN-ADL total scores will be used to test the following hypotheses:

Null hypothesis:

There is no difference between the fosmetpantotenate and placebo groups, as measured by the change in PKAN-ADL total score from baseline to the end of the 24-week double-blind treatment period, with adjustment for age group and baseline PKAN-ADL total score.

Alternate hypothesis:

There is a difference between the fosmetpantotenate and placebo groups, as measured by the change in PKAN-ADL total score from baseline to the end of the 24 week double-blind treatment period, with adjustment for age group and baseline PKAN-ADL total score.

That is:

H_0 : Change from baseline PKAN-ADL Total Score at Week 24 (fosmetpantotenate) = Change from baseline PKAN-ADL Total Score at Week 24 (Placebo) *estimated via repeated measure analysis, with adjustment for age group and baseline score*

H_1 : Change from baseline PKAN-ADL Total Score at Week 24 (fosmetpantotenate) \neq Change from baseline PKAN-ADL Total Score at Week 24 (Placebo) *estimated via repeated measure analysis, with adjustment for age group and baseline score*

The primary efficacy analysis will be based on the FAS population in the double-blind period of the study. For each patient, the change from baseline in PKAN-ADL total scores at Weeks 3, 6, 12, 18, and 24 of the double-blind period will be used for analysis. The treatment effect will be evaluated on the basis of a mixed model for repeated measures (MMRM) analysis to assess data from all visits simultaneously. The model will include fixed effects for treatment, age group (pediatric, adult), visit and treatment by-visit interaction, with visit as the repeating factor and patient as a random effect, and baseline PKAN-ADL total score as a covariate. The PKAN-ADL total score obtained prior to the first dose of investigational product will serve as each patient's baseline value.

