Patients with PKAN-ADL administration errors will be included in the Double-Blind FAS, but excluded from the PPS, as per [Section 4.5](#). Imputation rules for the data affected by the translation issue can be found in [Section 4.1](#).

The linear mixed-effect model will be implemented using PROC MIXED in SAS with the restricted maximum likelihood (REML) estimation method. An unstructured variance-covariance matrix will be used to model the within-patient errors. [Note: In the unlikely event that the computational algorithm fails to converge, the following structures will be executed in the order specified (essentially in decreasing order of complexity) until convergence is achieved: Toeplitz with heterogeneity, autoregressive with heterogeneity by Week, compound symmetry with heterogeneous variances by Week, autoregressive, Toeplitz, and compound symmetry without heterogeneous variances by Week.]

Significance tests will be based on least squares means (LSMs) using Type III sum of squares. The Kenward and Roger method will be used for calculating the denominator degrees of freedom for tests of fixed effects.

The PROC MIXED SAS coding is as follows:

```
proc mixed data=DATA;
    class TRT WEEK PATIENT;
    model C_score = BASE_score AGE TRT WEEK TRT*WEEK / solution
    ddfm=kr;
    repeated WEEK / subject=PATIENT type=un;

run;

where:
    TRT = treatment group (0 = placebo, 1 = fosmetpantotenate)
    WEEK = week 3, 6, 12, 18, 24
    AGE = age group (0=Pediatric, 1= Adult)
    C_score = change in score from baseline
    BASE_score = baseline score
```

The LSMS for each treatment, the difference between the LSMSs, and the standard error (SE) and 95% confidence interval (CI) associated with the difference will be reported at each study visit. The primary treatment comparison will be based on the test of contrast between treatment effects using the LSM estimate at Week 24, adjusted for baseline score and age group from the Type III analysis.

To estimate the mean change from baseline for PKAN-ADL total scores in each treatment group (placebo or fosmetpantotenate) at Week i ($i = 3, 6, 12, 18$, and 24), the following estimate statement (as an example) will be utilized:

```
estimate 'Placebo Group at Week 24'
    intercept 1
    AGE        <proportion in age group=0  proportion in age group=1>
    BASE_score <mean of BASE_score>
    TRT        1 0
    WEEK       0 0 0 0 1
    TRT*WEEK   0 0 0 0 1
                0 0 0 0 0 / cl;

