4.10.1.1 Sensitivity Analysis

To check that primary efficacy findings are robust, sensitivity analyses will be performed, as follows:

- The MMRM described in [section 4.10.1](#) will be repeated using the PPS, and presented in a similar manner. Of note, patients who had a PKAN-ADL administration error will be excluded from the PPS.
- In addition, analysis of covariance (ANCOVA) models will be applied to change from baseline in PKAN-ADL total scores assessed after 3, 6, 12, 18, and 24 weeks of treatment. For each week analyzed, the model will include treatment and age group (pediatric, adult) as fixed effects, and baseline PKAN-ADL total score as a covariate.

The ANCOVA analysis will be performed for the Double-Blind FAS using PROC GLM in SAS. The models will be run using the observed case (OC) and last-observation-carried-forward (LOCF) procedure to account for incomplete data. In each case, estimates of adjusted treatment means and the adjusted mean difference between treatment groups will be presented at each time point, along with the two-sided 95% CIs and p-values for treatment comparisons.

The LOCF procedure will be applied for post-baseline observations of the PKAN-ADL total score in which more than 20% of the items are missing and cannot be imputed in the manner described in [Section 4.1](#). The last observed post-baseline PKAN-ADL total score, including those from unscheduled visits, will be imputed to replace the missing value of PKAN-ADL total score.

The PROC GLM SAS coding, to be run for each visit and each OC/LOCF procedure, is as follows:

```
proc glm data=DATA;  
    class TRT AGE;  
    model week_x_total=base_score TRT AGE / solution;  
    lsmeans TRT/ pdiff stderr;
```

run;

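### Does scoring the PKAN-ADL baseline on 11 items, and later visits on 12, for two patients distort the primary result?

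*SAP*

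**What the plan says.** SAP 4.1 sets a general rule: when at least 80% of a scale's items are present, the total is the sum of the available items scaled up to the full number of items. It then deals with the translation fault: "There are two patients who had a question (item) on the PKAN-ADL mistranslated for screening and baseline visits". For FAS analyses, "the values for this item will be rendered invalid, set to missing, and the PKAN-ADL total score will be prorated"; the values as first recorded appear, flagged, in a listing.

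SAP 4.10.1 points back to this rule ("Imputation rules for the data affected by the translation issue can be found in" SAP 4.1). It defines the ordinary total: "To compute the total score, responses are summed across the 12 items", each scored 0 to 4. The primary MMRM uses change from baseline at Weeks 3, 6, 12, 18 and 24, "and baseline PKAN-ADL total score as a covariate". The same section plans improvement / no change / worsening tables, for which "a chi-squared test will be performed at each post-baseline visit to determine treatment differences".

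The affected patients stay in the FAS. SAP 4.10.1.1 repeats the MMRM on the Per-Protocol Set (PPS): "Of note, patients who had a PKAN-ADL administration error will be excluded from the PPS". SAP 4.4 limits that set to "FAS patients who complete the double-blind study without any major protocol violations".

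**The concern.** A change score should compare like with like. Here baseline stands on 11 items and the later totals on 12. If the lost item is typically better or worse than the patient's other items, the difference appears as improvement or worsening that did not occur. Because the fault is at baseline, it does not stay at one visit. It enters all five change scores and the baseline covariate.

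No planned FAS run on the total score uses the same items throughout: the MMRM, ANCOVA, tipping-point, subgroup and category analyses all take the same baseline. The PPS run drops these two patients together with non-completers and other major deviators, so a gap between FAS and PPS could not be traced to this issue. The sentence that voids the item also names no visit, so a programmer might void it at every visit. At stake would be the primary estimate of a pivotal trial with about 82 patients.

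**Working it through.** **Inputs.** 12 items scored 0 to 4 (SAP 4.10.1); proration rule and two affected patients (SAP 4.1); entry score of at least 6 (Protocol 7.1); 37 per arm, SD 4.5, target difference 3, two-sided alpha 0.05, 82 randomized (SAP 4.2), so about 41 per arm at 1:1.

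**The plan's own figure.** SE = 4.5 × √(2/37) = 1.046. A t-test with 72 degrees of freedom and noncentrality 3/1.046 has 80.8% power, which agrees with the stated figure of about 80%. 74/0.9 = 82.2, which agrees with 82.

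**Does proration apply?** 11/12 = 91.7%, above the 80% threshold. Yes.

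**Offset per patient.** Let S be the baseline sum of the 11 valid items and x the true baseline score on the lost item.
- True baseline = S + x; prorated baseline = 12S/11.
- Computed change = true change + e, where e = (S + x) − 12S/11 = x − S/11.
- So e is the same at every visit.
- Eligibility rested on the recorded total, which included the faulty item. Taking baseline equal to screening, a recorded total of at least 6 requires S ≥ 2. That leaves 43 × 5 = 215 patterns of (S, x).
- Extremes: e = −4.00 (S = 44, x = 0) and e = +3.82 (S = 2, x = 4).
- e = 0 in four patterns: (11,1), (22,2), (33,3) and (44,4).

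**Shift in the raw treatment difference.** The worst layout is both patients in one arm with the same sign, or one in each arm with opposite signs. The shift is then 2e/n:

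| Size of e | n = 41 per arm (SE 0.994) | n = 37 per arm (SE 1.046) |
|---|---|---|
| 1 | 0.049 (0.049 SE) | 0.054 (0.052 SE) |
| 4 | 0.195 (0.196 SE) | 0.216 (0.207 SE) |

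Against the 3-point target, at n = 37, this is 1.8% (0.054/3) and 7.2% (0.216/3). One patient in each arm with the same sign nearly cancels.

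**Effect on the test at 37 per arm.** A shift of 0.054 towards the null takes power from 80.8% to 79.3%; a shift of 0.216 takes it to 74.7%. With no true effect, the rejection rate goes from 5.00% to 5.03% or 5.48%.

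**With baseline as covariate.** Let b be the slope of the post-baseline score on baseline, which the documents do not give. The prorated baseline is the true baseline minus e, so the adjusted value moves by b × e and the shift is 2be/n. At an assumed b = 0.7 this is 0.034 to 0.038 (1 point) and 0.137 to 0.151 (4 points). Simulations with assumed b of 0.8 to 1.0 and baseline SD of 6 to 12 gave mean shifts of 0.043 to 0.054 for 1 point and 0.12 to 0.20 for the extremes. Single simulated data sets with the extreme offset came close to 0.5.

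**Would same-item scoring be better?** If the item is stable, the post-baseline total also moves by −e, so the adjusted value moves by −e + be = (b − 1)e. That is zero only at b = 1. If the item's deviation from the other items varies over time with equal variance, same-item scoring has the smaller mean squared error only when the correlation between its baseline and Week 24 deviations exceeds 1/(2b): 0.50 at b = 1 and 0.71 at b = 0.7. The documents do not give that correlation. In an assumed item-level simulation, same-item scoring did better when 10–20% of items moved a point (error 0.30–0.45 against 0.58–1.10). Results were mixed when 40–80% moved (0.58–0.90 against 0.53–1.04).

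**Category tables.** A truly stable affected patient misses the no-change category in 211 of the 215 patterns (a count of patterns, not a probability). Each patient is 1/41 = 2.4 to 1/37 = 2.7 percentage points of an arm.

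**The case for a change.** The strongest case for acting is that this is not routine missing data. A single item missing at Week 12 affects one visit; this fault is carried into all five. The sponsor thought the two patients important enough for a rule of their own, so the rule might as well name the visits. Two programmers could otherwise derive different primary values, and settling the point after unblinding invites questions. One sentence and one extra MMRM run would be cheap.

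Part of this stands. The mismatch is real, no FAS total-score run isolates it, and a borderline result could in principle be touched. The rest is weaker:

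- The ambiguity is thin. SAP 4.1 places the fault at screening and baseline, and SAP 4.10.1 ties the rule to the affected data. Nothing describes Weeks 3 to 24 as affected, so an analyst would void the item at the first two visits only.
- The same 11-against-12 comparison arises under the general rule for any patient with one item missing at baseline. Scoring these two differently would depart from that rule and discard valid later responses.
- The item-level FAS tables in SAP 4.10.1 compare each item with itself, so they do not share the mismatch.
- The PPS run does not isolate the issue, but it does show the result without these patients.
- The category tests lie outside the gatekeeping sequence and are exploratory under SAP 4.10.4.

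**Conclusion.** The observation is accurate and no change to the plan follows. The SAP identifies the fault, voids the invalid values, scores the patients by its general rule, keeps them in the FAS as randomized and leaves them out of the PPS. What remains is baseline measurement error in two of about 82 patients, with no expected direction between arms. It is worth about 0.05 points on the raw treatment difference for a 1-point offset in both, and about 0.2 points at the extreme of the scale, against a target of 3 points and a standard error of about 1.

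These figures assume the least favourable layout of the two patients, arms of 37 to 41, and the planning SD of 4.5. The extreme needs both patients at the top score on all 11 other items and zero on this one. The 0.2 is not a strict bound for a single data set in the adjusted model. The alternative scoring has no clear gain: which version is more accurate depends on a slope and an item correlation that the documents do not give. Recording the visit-specific derivation in the programming specification is ordinary practice and needs no SAP amendment.
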